symptomatic treatment (eg, antihistamines, NSAIDs, narcotics); prophylactic medications indicated for ≤24 hours. Grade 3 Prolonged (eg, not rapidly responsive to symptomatic treatment and/or brief interruption of infusion); recurrence of symptoms following initial improvement; hospitalization indicated - The infusion should be discontinued and no further ANV419 will be administered at that visit. Administer diphenhydramine 50 mg IV and remain at bedside and monitor the patient until resolution of symptoms. - Premedication will be instituted in patients who experience an allergic reaction to study drug. - Immediately discontinue infusion of ANV419. Begin an IV infusion of normal saline, and treat the patient as follows: - Recommend bronchodilators, epinephrine 0.2 to 1 mg of a 1:10,000 solution for subcutaneous administration or 0.1 to 0.25 mg of a 1:10,000 solution injected slowly for IV administration, and/or diphenhydramine 50 mg IV with methylprednisolone 100 mg IV (or equivalent), as needed. - Patient should be monitored until the Investigator is comfortable that the symptoms will not recur.			
 (eg, antihistamines, NSAIDs, narcotics); prophylactic medications indicated for ≤24 hours. Grade 3 Prolonged (eg, not rapidly responsive to symptomatic treatment and/or brief interruption of infusion); recurrence of symptoms following initial improvement; hospitalization indicated (eg, antihistamines, NSAIDs, narcotics); prophylactic medications bedside and monitor the patient until resolution of symptoms. Premedication will be instituted in patients who experience an allergic reaction to study drug. Immediately discontinue infusion of ANV419. Begin an IV infusion of normal saline, and treat the patient as follows: Recommend bronchodilators, epinephrine 0.2 to 1 mg of a 1:1000 solution for subcutaneous administration or 0.1 to 0.25 mg of a 1:10,000 solution injected slowly for IV administration, and/or diphenhydramine 50 mg IV with methylprednisolone 100 mg IV (or equivalent), as needed. Patient should be monitored until the Investigator is comfortable that the symptoms will not recur. 			
NSAIDs, narcotics); prophylactic medications indicated for ≤24 hours. Grade 3 Prolonged (eg, not rapidly responsive to symptomatic treatment and/or brief interruption of infusion); recurrence of symptoms following initial improvement; hospitalization indicated bedside and monitor the patient until resolution of symptoms. - Premedication will be instituted in patients who experience an allergic reaction to study drug. - Immediately discontinue infusion of ANV419. Begin an IV infusion of normal saline, and treat the patient as follows: - Recommend bronchodilators, epinephrine 0.2 to 1 mg of a 1:10,000 solution for subcutaneous administration or 0.1 to 0.25 mg of a 1:10,000 solution injected slowly for IV administration, and/or diphenhydramine 50 mg IV with methylprednisolone 100 mg IV (or equivalent), as needed. - Patient should be monitored until the Investigator is comfortable that the symptoms will not recur.	(eg, antihistamines,	administered at that visit. Administer diphenhydramine 50 mg IV and remain at	
prophylactic medications indicated for ≤24 hours. Grade 3 Prolonged (eg, not rapidly responsive to symptomatic treatment and/or brief interruption of infusion); recurrence of symptoms following initial improvement; hospitalization indicated - Premedication will be instituted in patients who experience an allergic reaction to study drug. - Immediately discontinue infusion of ANV419. Begin an IV infusion of normal saline, and treat the patient as follows: - Recommend bronchodilators, epinephrine 0.2 to 1 mg of a 1:1000 solution for subcutaneous administration or 0.1 to 0.25 mg of a 1:10,000 solution injected slowly for IV administration, and/or diphenhydramine 50 mg IV with methylprednisolone 100 mg IV (or equivalent), as needed Patient should be monitored until the Investigator is comfortable that the symptoms will not recur.	NSAIDs, narcotics);		
orade 3 Prolonged (eg, not rapidly responsive to symptomatic treatment and/or brief interruption of infusion); recurrence of symptoms following initial improvement; hospitalization indicated to study drug. Immediately discontinue infusion of ANV419. Begin an IV infusion of normal saline, and treat the patient as follows: Recommend bronchodilators, epinephrine 0.2 to 1 mg of a 1:1000 solution for subcutaneous administration or 0.1 to 0.25 mg of a 1:10,000 solution injected slowly for IV administration, and/or diphenhydramine 50 mg IV with methylprednisolone 100 mg IV (or equivalent), as needed. Patient should be monitored until the Investigator is comfortable that the symptoms will not recur.	prophylactic medications		
Prolonged (eg, not rapidly responsive to symptomatic treatment and/or brief interruption of infusion); recurrence of symptoms following initial improvement; hospitalization indicated saline, and treat the patient as follows: - Recommend bronchodilators, epinephrine 0.2 to 1 mg of a 1:1000 solution for subcutaneous administration or 0.1 to 0.25 mg of a 1:10,000 solution injected slowly for IV administration, and/or diphenhydramine 50 mg IV with methylprednisolone 100 mg IV (or equivalent), as needed. - Patient should be monitored until the Investigator is comfortable that the symptoms will not recur.	indicated for ≤24 hours.		
rapidly responsive to symptomatic treatment and/or brief interruption of infusion); recurrence of symptoms following initial improvement; hospitalization indicated - Recommend bronchodilators, epinephrine 0.2 to 1 mg of a 1:1000 solution for subcutaneous administration or 0.1 to 0.25 mg of a 1:10,000 solution injected slowly for IV administration, and/or diphenhydramine 50 mg IV with methylprednisolone 100 mg IV (or equivalent), as needed. - Patient should be monitored until the Investigator is comfortable that the symptoms will not recur.	Grade 3	- Immediately discontinue infusion of ANV419. Begin an IV infusion of normal	
symptomatic treatment and/or brief interruption of infusion); recurrence of symptoms following initial improvement; hospitalization indicated subcutaneous administration or 0.1 to 0.25 mg of a 1:10,000 solution injected slowly for IV administration, and/or diphenhydramine 50 mg IV with methylprednisolone 100 mg IV (or equivalent), as needed. - Patient should be monitored until the Investigator is comfortable that the symptoms will not recur.	Prolonged (eg, not		
and/or brief interruption of infusion); recurrence of symptoms following initial improvement; hospitalization indicated slowly for IV administration, and/or diphenhydramine 50 mg IV with methylprednisolone 100 mg IV (or equivalent), as needed. - Patient should be monitored until the Investigator is comfortable that the symptoms will not recur.			
of infusion); recurrence of symptoms following initial improvement; hospitalization indicated methylprednisolone 100 mg IV (or equivalent), as needed. - Patient should be monitored until the Investigator is comfortable that the symptoms will not recur.			
of symptoms following initial improvement; hospitalization indicated - Patient should be monitored until the Investigator is comfortable that the symptoms will not recur.			
initial improvement; symptoms will not recur. hospitalization indicated			
hospitalization indicated			
		symptoms will not recur.	
I tor clinical seguelae (eg. I For Grade 3 or any Grade 4 allergic reaction)			
	for clinical sequelae (eg,	For Grade 3 or any Grade 4 allergic reaction:	
renal impairment, - ANV419 will be permanently discontinued for prolonged Grade 3 or any Grade			
pulmonary infiltrates). 4 allergic reaction.	pulmonary infiltrates).		
- Patients may not continue to receive reference therapy in the absence of disease	Crede 4		
Grade 4 progression and/or intolerable AEs. Life the state in a second of the treatment of			
Life-threatening - Investigators should follow their institutional guidelines for the treatment of			
consequences; urgent anaphylaxis.		± *	
intervention indicated. Remain at bedside and monitor patient until recovery from symptoms. AE = adverse event; IV = intravenous(Iy); NSAID = nonsteroidal anti-inflammatory drug; PO = orally.			

5.4.5 Dose Modification Guidelines

AEs (both serious and non-serious) potentially related to ANV419, pembrolizumab, or ipilimumab may represent an immunologic etiology. These AEs may occur shortly after the first dose or several months after the last dose.

If a patient experiences TEAEs that may be related to ANV419 alone or in combination with pembrolizumab or ipilimumab, ANV419 doses might be reduced if applicable, interrupted, or permanently discontinued and all changes must be reported in the Case Report Form (CRF). All ≥Grade 3 AEs considered possibly, probably, or definitely related to study drug(s) must be

discussed with the Investigator and Sponsor. During Cycle 1, dose interruption should be avoided if a patient has not experienced a ≥Grade 2 TEAE related to study drug. In subsequent cycles, dose interruptions and/or discontinuation are permissible following discussion between the Investigator and the Sponsor or designee.

5.4.5.1 Dose Modification and Management Guidelines for adverse events related to ANV419 in Monotherapy Arms

General principles

Common adverse events that have been reported with ANV419 include, but are not limited to pyrexia, liver enzyme elevations, lymphopenia, nausea/vomiting, and low-grade CRS. Appropriate supportive care or pre-medication is recommended to manage ANV419 related side effects, and to maintain ANV419 dose-intensity.

For patients enrolled in Arm A1 (), dose reduction is not permitted but modification of infusion rate and/or dose delay is allowed in the event of ANV419 related toxicities. For patients enrolled in Arm A2 (), dose reduction to is permitted in addition to modification of infusion rate and/or dose delay. Dose re-escalation of ANV419 to the randomized dose can be considered for AEs that are self-limiting and under close monitoring. If re-escalation is not tolerated, then ANV419 should be reinstated at reduced dose.

Treatment may be delayed for up to ______ to allow for resolution of ANV419 related toxicities and for up to ______ for non-ANV419 related/unexpected toxicities (i.e., hip fracture). If treatment cannot be resumed within this time frame, the patient will be permanently discontinued from study.

The section below provides specific guidelines for the management of related ANV419 toxicities. The recommendations are not intended to serve as rigid guidelines or to replace clinical judgement.

Pyrexia

Episodes including recurring episodes of pyrexia are observed in patients receiving ANV419. Pyrexia may be accompanied with chills. Pyrexia typically presents 4 to 6 hours post ANV419 infusion and lasts between 1 and 4 days. Some patients are experiencing pyrexia on each cycle, others only on one cycle, not necessarily the first one. Pyrexia and chills typically resolve with standard supportive treatment.

To minimize the pyrexia in patients with ANV419, anti-pyretic treatment (e.g., paracetamol or acetaminophen) should be administered shortly after ANV419 infusion or as pre-medication and repeated every 8 hours as needed.

Table 12: Management guidelines for pyrexia related to ANV419

Pyrexia	Recommended management	Dose modification
First occurrence, or recurrent pyrexia	 Consider premedication with paracetamol/acetaminophen if not implemented Exclude other reasons for pyrexia Administer anti-pyretic treatment with NSAID and/or acetaminophen/paracetamol Encourage oral hydration 	Withhold ANV419 until < Grade 1; continue at same dose
Recalcitrant (refractory) pyrexia	Consider adding oral corticosteroids	If pyrexia cannot be successfully managed to a tolerable level: permanently discontinue if

Cytokine release syndrome

For management guidelines of cytokine release syndrome (CRS), refer to Table 17 further below.

Lymphopenia

ANV419 induces transient lymphopenia assumed related to lymphocyte redistribution and sequestration from the peripheral blood. This is an expected pharmacodynamic effect of ANV419 and was not associated with any increase in infection, or other clinical sequalae. In all cases, the observed lymphopenia was self-limiting with lymphocyte count rebounding around and a dose dependent increase of lymphocyte expansion over time. Patients with prolonged or persistent lymphopenia should be thoroughly investigated for alternative etiologies than ANV419 related.

Table 13: Management guidelines for lymphopenia related to ANV419

CTCAE v5.0	Recommended management	Dose modification
Any grade	None	No dose modification
Note: for prolonged or persistent lymphopenia, alternative etiologies of lymphopenia should be excluded		

AST and/or ALT elevations with early onset (Cycle 1-2)

Transient elevation of hepatic transaminases are observed with ANV419 and are considered to occur in the context of IL-2 mediated AEs. The transient elevations are usually asymptomatic, mild or moderate in severity, typically not associated with increased total bilirubin and alkaline phosphatase, resolve spontaneously without treatment, and are predominantly occurring in the first two cycles. For AST and/or ALT elevations beyond cycle 2, and for AST/ALT elevations in the

context of total bilirubin increase, follow the adverse event management guidance for hepatitis (Table 15).

Table 14: Management guidelines for AST and/or ALT elevations with early onset related to ANV419

	Recommended management	Dose modification
AST or ALT > 3 but ≤ 5 × ULN	 LFT monitoring: Repeat lab every 3 days If no improvement within 7 days, initiate treatment with steroids Consider imaging for obstruction Exclude non-inflammatory etiologies 	Withhold ANV419 until ≤ Grade 1 or baseline; continue at same dose
AST or ALT > 5 × but ≤ 8 × ULN	 LFT monitoring: Repeat lab every 3 days If no improvement within 7 days, initiate treatment with steroids Consider adding non-corticosteroid immunotherapy 	Withhold ANV419 until ≤ Grade 1 or baseline; continue at same dose
AST or ALT > 8 × ULN	 LFT monitoring: Repeat lab every 1-2 days If no improvement within 7 days, initiate treatment with steroids Consider adding non-corticosteroid immunotherapy Consult gastroenterologist 	Consider permanent discontinuation of ANV419

Hepatitis

Table 15: Management guidelines for hepatitis related to ANV419

(adapted from the ASCO management guidelines for Immune-Related Adverse Events; J Clin Oncol2021:36 4073-4126).

CTCAE v5.0	Recommended management	Dose modification
Grade 1	• Close monitoring (1-2 ×	Continue ANV419 at same dose
Asymptomatic (AST or	weekly)	
ALT > ULN to $3.0 \times$	• Exclude alternate etiologies	
ULN and/or total	(e.g., viral hepatitis, alcohol	
bilirubin > ULN to 1.5 ×	hepatitis)	
ULN	1 /	

Grade 2 Asymptomatic (AST or ALT > 3.0 to ≤ 5.0 × ULN and/or total bilirubin > 1.5 to ≤ 3.0 × ULN) Grade 3 AST or ALT 5.0-20.0 × ULN and/or total bilirubin 3-10 × ULN, OR symptomatic liver dysfunction; fibrosis by biopsy; compensated cirrhosis; and reactivation of chronic hepatitis	 Stop unnecessary medication and any potential hepatotoxic drugs Consider administration of steroids if no improvement in 3-5 days Increase monitoring frequency to every 3 days Consider adding mycophenolate mofetil if no improvement after 3 days Consider hepatology consult for Grade 2 and above Start steroids 1-2 mg/kg methylprednisolone or equivalents Consider liver biopsy Monitor labs daily 	Withhold ANV419 until ≤ Grade 1; continue at same dose Permanently discontinue ANV419
Grade 4 AST or ALT > 20.0 × ULN and/or total bilirubin > 10 × ULN OR decompensated liver function	Consider adding methylprednisolone 2 mg/kg/d equivalents	Permanently discontinue ANV419

Note: Combination of AEs suggestive of drug induced liver injury (DILI), with hepatocellular injury (AST or ALT $> 3.0 \times ULN$) accompanied by evidence of impaired hepatic function (total bilirubin elevation $> 2 \times ULN$), in the absence of evidence of initial biliary obstruction (i.e., significant elevation of ALP) or some other explanation of the injury (e.g., viral hepatitis, alcohol hepatitis), see FDA guidance, should lead to permanent discontinuation from treatment.

Other adverse events

For other adverse events deemed as clinically significant and for which no specific guidelines are provided, the following dose modifications should be followed (Table 16).

Table 16: Management guidelines for "other" ANV419 related adverse events

CTCAE v5.0	Dose modification
Grade 1	Continue at the same dose of ANV419
Grade 2	If tolerable: Continue at the same dose of ANV419;
	If intolerable: withhold ANV419 until \leq Grade 1 or baseline;
	reinstate ANV419 at the same dose
Grade 3	Withhold ANV419 until ≤ Grade 1 or baseline;
	1 st occurrence: reinstate ANV419 at the same dose
	2 nd occurrence or if not manageable: permanently discontinue if
	3rd occurrence: permanently discontinue ANV419
Grade 4	Permanently discontinue ANV419

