4.4 Discontinuation of study treatment

Discontinuation of a patient from study treatment may occur or any of the following reasons:

- The patient or legal representative (such as a parent or legal guardian) withdraws consent;
- Confirmed radiographic disease progression;

Note: A patient may be granted an exception to continue on treatment with confirmed radiographic disease progression if clinically stable or clinically improved. Such cases should be discussed by the Investigator or treating physician with the Sponsor.

Note: In certain circumstances, a patient experiencing disease progression per RECIST without clinical deterioration may be allowed to continue on treatment if the Investigator considers it in the patient's best interest and in agreement between the Investigator and Sponsor. If repeated tumor assessment within 4 to 8 weeks confirms progressive disease, the patient will need to be discontinued permanently from treatment.

- Occurrence of any medical condition or circumstance that exposes the patient to substantial risk and/or does not allow the patient to adhere to the requirements of the Protocol;
- Any SAE, clinically significant AE, DLT, severe laboratory abnormality, intercurrent illness, or other medical condition which indicates to the Investigator that continued participation is not in the best interest of the patient;
- Patients who meet Hy's law will be discontinued from treatment;
- Pregnancy;
- Requirement of prohibited concomitant medication;
- Patient failure to comply with Protocol requirements or study-related procedures;
- The patient is lost to follow-up; or
- Termination of the study by the Sponsor or the regulatory authority.

Patients who discontinue for reasons noted above other than progressive disease will have post-treatment follow-up for disease status until disease progression, initiation of a non-study cancer treatment, withdrawal of consent, or lost to follow-up. In addition, each patient, irrespective of disease progression, will be followed for survival by telephone (or public records when allowed as per local regulation) until death or study termination whichever occurs first. Study staff should make every effort to complete the full panel of assessments scheduled for the End of Study Visit in addition to disease evaluation as noted above (■■■ OR ≤30 days since last

dose of study drug). The reason for patient withdrawal must be documented in the electronic case report form (eCRF).

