4.5 Reasons for End of Study and withdrawal from study

Patients may withdraw consent at any time for any reason or be dropped from the study at the discretion of the Investigator should any untoward effect occur. In addition, a patient may be withdrawn by the Investigator or the Sponsor if enrollment into the study is inappropriate, the study plan is violated, or for administrative and/or other safety reasons.

Reasons for end of study and patient withdrawal from the study could be any of the following:

- Withdrawal of consent by the patient;
- Lost to follow-up;
- Death; or
- Study termination by Sponsor.

The study will be discontinued or terminated in case of an unacceptable risk, any relevant toxicity, or a negative change in the risk/benefit assessment. This might include the occurrence of AEs for which the character, severity, or frequency is new in comparison to the existing risk profile. In addition, any data deriving from other clinical studies or toxicology studies which negatively influence the risk/benefit assessment might cause discontinuation or termination of the study.

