5.5 Prior and Concomitant Medications and/or Procedures

5.5.1 Excluded Medications and/or Procedures

The following medications and procedures are prohibited during the Screening and study:

- Any investigational agent (including investigational device) other than ANV419, pembrolizumab, and ipilimumab;
- Antineoplastic systemic chemotherapy or biological therapy;
- Immunotherapy not specified in this Protocol;
- Radiation therapy;
 - Note: Radiation therapy to a symptomatic solitary lesion or to the brain may be allowed after discussion between the Investigator and Sponsor.
- Systemic glucocorticoids for any purpose other than to modulate symptoms from an event of clinical interest of suspected immunologic etiology;
 - Note: The use of physiologic doses of corticosteroids may be approved after consultation with the Sponsor.
- Live vaccines administered within 30 days of planned start of study drug; and
 - Note: Seasonal influenza vaccines for injection are generally inactivated flu vaccines and are permitted; however, intranasal influenza vaccines (eg, Flu-Mist) are live attenuated vaccines and are prohibited.
- Local surgery resulting from disease progression is prohibited; however, if indicated for palliative measure and after Investigator approval, local surgery may be permitted after the Patients who, in the opinion of the Investigator, require the use of any aforementioned treatments for clinical management should be removed from the study.

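### Sections 5.4.5.1 and 5.5.1 take two groups of patients off the study, in conflict with the follow-up rule in Section 4.4, so their scans and survival data may be lost

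*Protocol*

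**What the plan says.** Two passages of the protocol end study participation:

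- Section 5.4.5.1 (monotherapy arms), on delays beyond the permitted limit: "If treatment cannot be resumed within this time frame, the patient will be permanently discontinued from study". The limits are redacted; the consequence is not.
- Section 5.5.1, after its list of excluded treatments: "Patients who, in the opinion of the Investigator, require the use of any aforementioned treatments for clinical management should be removed from the study". The list includes systemic anticancer therapy, radiation and systemic glucocorticoids, with stated exceptions.

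Section 4.4, which concerns stopping study treatment, says otherwise. Its reasons include "Requirement of prohibited concomitant medication" and also "Any SAE, clinically significant AE, DLT, severe laboratory abnormality, intercurrent illness, or other medical condition" where the investigator judges that continuing is not in the patient's interest. It then states: "Patients who discontinue for reasons noted above other than progressive disease will have post-treatment follow-up for disease status until disease progression". That follow-up also ends at a non-study cancer treatment, withdrawal of consent or loss to follow-up. On survival, "each patient, irrespective of disease progression, will be followed for survival by telephone". Footnote d of Tables 20 and 21 in Appendix A repeats both requirements.

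Section 4.5 introduces its list with "Reasons for end of study and patient withdrawal from the study could be any of the following" and names consent withdrawal, loss to follow-up, death and sponsor termination. The paragraph before the list also gives the investigator discretion to drop a patient after an untoward effect, and allows withdrawal for administrative or other safety reasons.

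**The concern.** Stopping a drug and ending data collection are different events, and the endpoints depend on keeping them apart. Where one section stops treatment and another ends participation, a site has two instructions and can follow either. If it follows the second, the patients lost are not a random subset. They are patients whose toxicity or other delay did not resolve in time, or who needed other treatment.

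What could be lost is the post-treatment scans behind ORR and PFS and the survival calls behind OS. Section 5.4.5.1 governs the Part 1 arms, where ORR is primary. It also gives the two arms different options short of delay: Arm A2 may reduce the dose and Arm A1 may not. Overruns, and any data lost with them, could therefore differ between the randomised arms.

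**Working it through.** **Step 1. The passages side by side.**

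| Situation | Ends study participation | Stops treatment, follow-up continues |
|---|---|---|
| Needs a prohibited treatment | Protocol 5.5.1 | Protocol 4.4 names this trigger; Appendix A footnote d |
| Delay beyond the limit, monotherapy | Protocol 5.4.5.1 | Not named in 4.4; the nearest item is the adverse-event reason, which rests on investigator judgement. The survival sentence covers each patient |
| Hold beyond 42 days, combination arms | None | Protocol 5.4.5.4: the drugs stop |
| Stops under the adverse-event tables (11, 15, 16, 17) | None | ANV419 or study drug stops; 4.4 remains in force |

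The conflict is exact for prohibited treatment. For delay overruns it is a conflict with the survival sentence in 4.4 and a mismatch with the parallel combination-arm rule.

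**Step 2. What the SAP does with a patient lost this way.**

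- *ORR.* The Efficacy Population (SAP 3.2.2) needs at least one post-baseline tumour assessment. A patient lost before the first scan leaves the denominator. A patient lost later stays in as a non-responder unless a response was already recorded, so any later response is missed.
- *PFS.* SAP Table 3-3 censors at the last evaluable scan, or at first dose if there is none.
- *OS.* SAP 3.4.2.5 censors at the date last known alive.

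If the prohibited treatment is a new anticancer therapy, 4.4 itself ends disease follow-up and Table 3-3 censors PFS at the last evaluable scan before it. The added loss is then survival follow-up.

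**Step 3. The plan's own figures (protocol 8.2.1).** With a uniform prior and r responses in n patients, the posterior is Beta(1 + r, 1 + n − r), with mean (r + 1)/(n + 2). For r = 0 the upper 90% limit is 1 − 0.05^(1/(n + 1)).

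- 0/15: mean 1/17 = 5.88%, interval 0.32% to 17.07%. Plan: 5.9% (0.3%, 17.1%).
- 0/30: mean 1/32 = 3.13%, interval 0.17% to 9.21%. Plan: 3.1% (0.2%, 9.2%).

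Both reproduce.

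**Step 4. Sensitivity.** The number lost is my assumption, and so is applying these calculations to the Efficacy Population.

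| Case | Mean | Upper 90% limit |
|---|---|---|
| 0/15 | 5.9% | 17.1% |
| 0/14 | 6.3% | 18.1% |
| 0/13 | 6.7% | 19.3% |
| 0/12 | 7.1% | 20.6% |
| 0/30 | 3.13% | 9.21% |
| 0/27 | 3.45% | 10.15% |

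Losing 3 of 30 before a first scan moves the upper limit from below to just above the 10% success threshold. For the Clopper-Pearson 95% interval that the SAP will report, the upper limit goes from 11.57% (0/30) to 12.77% (0/27).

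The monitoring rule is P(ORR > 10%) of about 95%:

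- One non-responder leaving the denominator: 4/20 gives 0.948 and 4/19 gives 0.957; 3/14 gives 0.944 and 3/13 gives 0.956.
- One later response missed in a full arm: 4/15 gives 0.983 and 3/15 gives 0.932. Observed ORR falls by 1/15 = 6.7 percentage points.

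A single patient can move a case across the boundary in either direction. PFS and OS have no planned figure to recompute.

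**The case against.** The strongest reply is that neither passage says follow-up ends. The protocol uses the word study loosely. The End of Study visit can fall within 30 days of the last dose, it is the same visit for patients who leave early, and the safety and survival follow-up columns come after it in the schedules. Section 4.4 itself refers to that visit and to patient withdrawal while requiring survival follow-up. Leaving the study could therefore mean having the End of Study visit and then entering follow-up. This stands to the extent that data loss is a possible consequence of a literal reading, not a certain one.

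Second, Section 4.5 does permit withdrawal for an untoward effect, so its four-item list cannot be read as complete. This also stands, and it means that editing 5.4.5.1 and 5.5.1 alone would leave a gap. It does not remove the conflict: discretion for the investigator differs from the automatic exit in 5.4.5.1.

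Third, 5.5.1 exempts glucocorticoids given for an event of suspected immunologic cause, and new anticancer therapy already ends disease follow-up. Both points are correct and narrow the loss of scans under 5.5.1.

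Finally, 5.4.5.1 says that its recommendations are not rigid. That remark follows the delay rule and refers to the toxicity-specific guidance below it, so it does not soften the rule.

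**Conclusion.** The inconsistency is real and is in current text. Read literally, it may cost scans and survival data for two groups: monotherapy patients over the delay limit, and patients who need a prohibited treatment. The resulting censoring of PFS and OS could be related to outcome, and the ORR denominator or a later response could be affected.

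A reader might infer that all patients who stop for toxicity would lose follow-up. The documents do not support that: the adverse-event tables and the combination-arm rule stop drugs only and leave 4.4 in force. A reader might also take the earlier phase 1 study's 97% rate of drug-related events (33 of 34) as a guide to the number affected. That rate counts events of any grade, not delay overruns, and the documents give no count. Nor does the use of iRECIST show that responses after dosing stops were expected; Appendix D ties it to responses after pseudo-progression.

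The realised effect is probably small. The SAP reports no responses in Part 1 (Section 5), and survival follow-up was stopped when the trial did not proceed (Section 1). This does not show that no data were lost before then. The arithmetic shows sensitivity to one to three patients under assumed losses; it does not estimate what happened.

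**What to change.** - In 5.4.5.1 and 5.5.1, state the consequence as discontinuation from study treatment, with follow-up under Section 4.4.
- In 4.5, state that withdrawal for an untoward effect or safety reason means stopping treatment, and that follow-up continues unless the patient withdraws consent.
- Leave every delay limit and treatment-stopping rule unchanged.
- In the CSR, report by arm how many patients left the study under the delay rule or the prohibited-treatment rule. SAP 3.3.1 already summarises discontinuations and their reasons, so this needs at most a finer breakdown of reasons.

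The protocol edits are short and add no visits, because 4.4 and Appendix A already require the follow-up. They do need an amendment through the review and approval process in Section 11.1. As the trial stopped after Part 1, the CSR count is the useful step now. The wording matters if this protocol is reopened or its text is reused.
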